# 7.1.2 Adjusting anti-hypertensive therapy

Within the same encounter, a second 30-minute teaching session will be delivered to participants regarding the treatment algorithm for titration of anti-hypertensive medications. Each participant will have an individualized three-step treatment plan that is developed with their physician, and which is based on their recorded home BP values during the measurement week of each month. The choice of anti-hypertensive agent and dose is at the physician's discretion. Participants who record 50% or more values above target during their measurement week will move to the next step of their

treatment plan (either increasing their home dose of RAAS inhibitor or contacting their physician for a new medication prescription). In this way, there is no requirement for an additional clinic encounter. Once the three steps have been completed, the participants will return to the clinic to create a new three-step plan. In consultation with our patient partners, we established that a minimum of 8 BP values during a measurement week (equivalent to 4 out of 7 measurement days) would be required in order for any medication changes to be made. If a participant is unable to complete the requisite number of BP measurements, they will be given an opportunity to repeat the set of BP measurements the following week (as opposed to waiting until the following month).

### 7.2 Control

Participants randomized to usual care (control group) will be asked to attend their scheduled clinic visit with their nephrologist for monitoring and treatment of their blood pressure. The physician who assessed them in the clinic will be notified to ensure that any planned changes to anti-hypertensive medications from their clinic visit are actioned.

# 8. Study procedures

As described in Section 5, potentially eligible patients will be approached about the study either at a regularly scheduled clinic visit or a few days prior to the visit. Full eligibility will be established at the clinic visit based on their blood pressure measurement that day. Eligible patients who are willing to participate in the trial will be consented and then randomized to determine treatment allocation. No treatment will be started until all of these steps have been completed. Participants will have three dedicated study visits embedded within their regularly scheduled clinic visits at baseline (day of randomization), 3 months and at 6 months (study completion). Participants in the self-management (intervention) group will have one additional study visit in close proximity to their baseline clinic visit for training.

## Visit 1 (Week 0)

All participants will attend a baseline research visit at which time a research nurse or coordinator will explain the study procedures and obtain written informed consent. All participants will be asked to complete a CRF regarding demographics (age, sex, gender identity), current medications (name, dose and frequency), and health conditions including diabetes, pre-existing cardiovascular disease (prior heart attack or stroke, coronary artery disease, peripheral arterial disease) and pre-existing hypertension. All participants will be asked to complete the Simple Lifestyle Indicator Questionnaire which includes questions about healthy eating, exercise, alcohol consumption and smoking. Height, weight and waist circumference will be measured. An automated clinic blood pressure measurement (BpTRU) will be taken with the participant left unaccompanied in the clinic room for 8 minutes during which time an average of 3 blood pressure measurements will be recorded after a 5-minute period of rest. This BP measurement approach is the current standard of care for all patients who attend the GN clinic and will serve as the baseline BP value. This research visit is anticipated to last one hour.

Participants who are randomized to self-management will be given the option of either: (i) completing the training on the same day as their clinic visit; or (ii) scheduling the training on a different day within 7 days of randomization. The training is anticipated to last between 30 and 60 minutes depending on how familiar patients are with measuring their own BP. As long as creatinine and electrolytes have been checked recently (within 4 weeks), there will be no need for additional blood tests at the baseline visit. All participants will be provided with a urine collection jar for 24-hour protein, creatinine and sodium excretion. Written instructions will be provided with the jar. The jar should be returned to the laboratory at The Ottawa Hospital or to the research team within 2 days. Expenses related to the research visit and return of the urine specimen (e.g., parking) will be reimbursed to each participant.

# Visit 2 (Week 12)

Each participant will have a clinic visit with their treating physician during which laboratory tests (including creatinine and potassium) will be repeated along with a BpTRU measurement. Participants will be evaluated for orthostatic hypotension by

measuring their BP while sitting followed by a BP measurement with the participant standing for 1 and 3 minutes. Orthostatic hypotension will be defined as a drop in systolic BP of at least 20 mmHg or a drop in diastolic BP of at least 10 mmHg. All participants will be asked to complete the Simple Lifestyle Indicator Questionnaire. A medication reconciliation will be performed as per standard of care in the clinic.

# Visit 3 (Week 24)

All participants will have a clinic visit with their nephrologist including medication update, a BpTRU measurement, weight and waist circumference, laboratory tests (creatinine and potassium), and a 24-hour urine collection for daily sodium and protein excretion. Participants will be evaluated for orthostatic hypotension as previously described. All participants will be asked to complete the Simple Lifestyle Indicator Questionnaire.

### Patient experience outcomes

Participants in the self-management arm will be asked to complete a short journal entry once during each measurement week. The purpose of this is to obtain a longitudinal evaluation of their experience during the 6 months of the trial. Participants will be asked to rank their confidence on a Likert scale with respect to measurement of BP, interpretation of the values, and the actions taken based on the treatment algorithm. Participants will be encouraged to provide additional information about their experience in a free-text box. At the end of the trial period, all participants in the self-management arm will be invited to participate in a semi-structured interview by phone. Our team of patient partners felt that a one-on-one interview would be superior to a group interview and would provide richer feedback about their personal experiences of participating in the study. Information from the journal entries will be used to identify themes that can be explored further during the interview.

# 9. Safety assessments

### 9.1 Potential risks to participants

Participants in the intervention arm could be at a higher risk of adverse events from more rapid escalation of their anti-hypertensive therapy. Serum creatinine and

potassium will be checked within 7 to 10 days of initiating a RAAS inhibitor. Laboratory tests will be rechecked within 7 to 10 days of increasing the dose of a RAAS inhibitor in the following situations: (i) previous serum potassium value ≥4.8 mmol/L; (ii) eGFR <30 mL/min; or (iii) physician discretion. Participants will be encouraged to contact the clinic staff outside of scheduled encounters if they develop symptoms indicative of low blood pressure (light-headedness, weakness). Sitting and standing BP will be measured at each study visit to look for evidence of orthostatic hypotension. Each participant will be provided with "sick day guidance" with respect to stopping their RAAS inhibitor during acute illness. Participants may feel apprehensive or overwhelmed about having to self-manage their blood pressure. The potential for participant burden has been a major focus for our team in development of this protocol. Our patient partners have provided feedback about each step of the process to mitigate this risk.

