### Methods

Self-management means that patients measure their BP at home and adjust the dose of their medications to a target BP value. A previous clinical trial conducted in patients without kidney disease showed that patients and their family doctors were able to successfully develop a self-management protocol. Working with our patient partners, we have adapted that protocol for patients with IgA nephropathy. The next step is to conduct a pilot clinical trial involving approximately 25 patients with IgA nephropathy who attend kidney clinics in Ottawa and Vancouver. Trial participants will be randomly chosen to either manage their BP using the self-management protocol or to be in the control group. Participants in the self-management group will be taught how to accurately measure their BP at home over a 7-day period each month. If most of these BP values are above target, they will contact the clinic for a new medication prescription

based on a 3-step plan which was developed with their doctor. Participants in the control group will have their BP measured and treated at clinic visits only. All participants will be followed for 6 months. At the end of the study period, we will measure BP and urine protein levels in all participants and compare these between the self-management and control groups. We will also interview participants in the self-management group to ask them about their experiences.

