### Safety outcomes:

- 1. Orthostatic hypotension (measured at clinic visits)
- 2. Change in estimated glomerular filtration rate (eGFR) during the study period
- 3. Hyperkalemia episodes (serum potassium >5.3 mmol/L)
- 4. Frequency of coordinator intervention required in the self-management arm due to protocol deviations/errors

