#### 5.2 Exclusion criteria

- Currently receiving immunosuppression or in need of urgent start immunosuppression (e.g., rapidly progressive glomerulonephritis or nephrotic syndrome).
- Kidney failure defined by the need for dialysis, kidney transplantation or eGFR
   <15 mL/min.

- Recent (within 3 months) history of acute myocardial infarction or stroke.
- Heart failure with reduced ejection fraction.
- Concomitant diabetic nephropathy on kidney biopsy.
- Pregnancy (or actively planning a pregnancy) or breastfeeding.
- Life expectancy <12 months.
- Allergy or intolerance to both an angiotensin converting enzyme inhibitor and angiotensin II receptor blocker.
- Severe hypertension requiring urgent treatment (>180/100 mmHg).

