### 7. Study treatments

Participants will be randomized 2:1 to self-management (intervention) or usual care (comparator). The current standard of care for patients with IgA nephropathy attending the Glomerulonephritis Clinic is to measure their blood pressure at scheduled clinic visits and make treatment decisions based on those values. Clinical guidelines recommend RAAS inhibitors as first-line therapy. Patients not requiring immunosuppression treatment are typically followed in the clinic every 4 to 6 months. Participants in the intervention and control group will be assessed in the clinic at baseline, at 3 months and at 6 months. In both groups, the dose of RAAS inhibitor will be progressively increased to achieve a systolic BP <120 mmHg. The use of other antihypertensive medications will be permitted in both groups at the discretion of the treating physician after the dose of RAAS inhibitor has first been maximized. For patients receiving other (non-RAAS inhibitor) antihypertensive therapy at the time of recruitment, these medications will be replaced by a RAAS inhibitor at study entry. As such, they will be receiving care at a level at or above the current standard of care. Patients in the intervention group will additionally measure their blood pressure at home and follow the algorithm as described below.

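### Nothing in the protocol tells staff when a participant raises a RAAS inhibitor dose at home, so the 7 to 10 day laboratory recheck in section 9.1 has no assured trigger

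*Protocol*

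**What the plan says.** Under Protocol section 7.1.2, a participant with at least half of the month's home readings above target moves to the next step of a three-step plan written with the physician. The step is "either increasing their home dose of RAAS inhibitor or contacting their physician for a new medication prescription". The section continues: "In this way, there is no requirement for an additional clinic encounter". The clinic next enters at the end of the plan: "Once the three steps have been completed, the participants will return to the clinic to create a new three-step plan".

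Section 9.1 requires creatinine and potassium within 7 to 10 days of starting a RAAS inhibitor, without condition. For a dose increase the rule is conditional: "Laboratory tests will be rechecked within 7 to 10 days of increasing the dose of a RAAS inhibitor in the following situations". The situations are (i) previous potassium of 4.8 mmol/L or more, (ii) eGFR below 30 mL/min, and (iii) physician discretion.

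Beyond these, section 8 schedules potassium and creatinine for everyone at Visit 2 (week 12) and Visit 3 (week 24).

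**The concern.** The 7 to 10 day clock starts at the dose increase. When the step is a new prescription, the physician knows the date. When the participant raises the dose of a drug already at home, section 7.1.2 attaches no contact to the step, so staff may not know that the clock has started.

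Section 9.1 itself names faster escalation as the risk particular to the intervention arm, and hyperkalaemia and eGFR change are listed safety outcomes. Section 1.5 adds that self-management has not been studied for safety in people with reduced kidney function. A missed recheck would leave a rise in potassium or a fall in eGFR unseen until the next scheduled visit, possibly after a further increase. The advice in section 9.1 to call about symptoms of low blood pressure would not reveal a raised potassium.

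**Working it through.** The plan gives no figure to reproduce here. The check has three parts.

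**1. Does any other text make staff aware of a home increase?**

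| Place in the Protocol | What it provides | Closes the gap? |
|---|---|---|
| Lay summary, Methods | "If most of these BP values are above target, they will contact the clinic for a new medication prescription" | No. It describes a new prescription, not an increase of a drug already held |
| 3.1, item 3 | Submitted readings compared with the monitor download at study end | No. No submission time or prompt review is stated, and it concerns readings, not doses |
| 3.2, Safety outcomes | "Frequency of coordinator intervention required in the self-management arm due to protocol deviations/errors" | No. It counts interventions and sets no duty to report a correct step |
| 7.1.1 | A call for persistent systolic values below 100 or above 180 mmHg; an instruction sheet | No for the call; the sheet's content is not shown |
| 8, Patient experience outcomes | Monthly journal ranking confidence, with free text | No. It is not a dose report |
| 9.3 | Adverse event capture | No. A planned dose step is not an adverse event |

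**2. Can people who need the recheck be enrolled and given a home increase?** Section 5.2 excludes "Kidney failure defined by the need for dialysis, kidney transplantation or eGFR" below 15 mL/min and sets no potassium limit, so eGFR 15 to 29 and any potassium may enter. Section 7 permits other agents only "after the dose of RAAS inhibitor has first been maximized", so someone below the maximum dose is directed to RAAS inhibitor escalation first. Section 7.1.2 leaves agent and dose to the physician, who may therefore choose which steps are home increases.

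**3. Would the scheduled laboratory tests fall in the window anyway?** Week 12 is day 84 and week 24 is day 168. The protocol does not fix the dates of measurement weeks, so two readings were tried. In both, training takes place 0 to 7 days after randomization (section 8), a 7-day practice week follows, then 7-day measurement weeks, with each step on the day after a measurement week.

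*Every 4 weeks.* Steps fall on day 14 + 28k, plus any training delay.
- Training on day 0: steps on days 14, 42 and 70; gaps to day 84 are 70, 42 and 14 days.
- Training on day 7: steps on days 21, 49 and 77; gaps are 63, 35 and 7 days.
- After week 12, with training on day 0: steps on days 98, 126 and 154; gaps to day 168 are again 70, 42 and 14 days.

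On this calendar, the return to clinic after three steps falls due no earlier than day 70.

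*First week of each calendar month.* 365 randomization dates × 8 training delays = 2,920 schedules.
- 2,376 schedules have two possible steps before day 84, with gaps of 33–62 and 2–31 days.
- 544 have three, with gaps of 60–70, 29–42 and 1–11 days.
- Steps other than the last: 2,376 × 1 + 544 × 2 = 3,464. Their gaps are 29–70 days, and none is within 7 to 10 days.
- Last steps: 302 + 82 = 384 of 2,920 (13%) fall within 7 to 10 days, by chance.

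*Size of the arm.* 25 × 2/3 = 16.7, about 17 participants. The documents do not say how many will meet (i) or (ii) and still have a dose increment left.

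**The case against.** The strongest reply is that the safeguard exists and only its mechanics are unstated. The recheck is compulsory under (i) and (ii). The physician writes the plan with the participant, and section 8 expects creatinine and electrolytes within 4 weeks of baseline, so those criteria are normally known at that moment and the tests can be ordered then. This stands, and it narrows the point. For participants who meet (i) or (ii) at baseline, the gap opens only if nothing was ordered in advance. It does not cover a criterion first met later, or (iii), which needs the physician to know of the step. Nor does the protocol ask for advance ordering.

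It can also be said that the lay summary, the submitted readings and the count of coordinator interventions suggest that someone is watching, and that the instruction sheet may already ask for a call. That makes an unobserved step less likely, but none of it states a duty to report.

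A reader might go further and infer that section 7.1.2 allows unreported dose changes. It does not say so. It waives an extra clinic encounter and is silent on notification. Nor do the schedule counts mean that 87% of rechecks would be missed. They show only that visit laboratory tests cannot stand in for the recheck, not how often it would fail to happen.

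**Conclusion.** The point holds in limited form. A participant who follows section 7.1.2 exactly can leave staff unable to time a check that section 9.1 requires, and no other text in the protocol supplies the missing link. How often this would happen cannot be estimated: it needs an increment left on a RAAS inhibitor already held, a section 9.1 criterion, no tests ordered ahead and no contact by the participant. Starting a RAAS inhibitor is not affected, nor is any step that needs a new prescription.

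The conclusion assumes that the instruction sheet, which is not shown, does not already require notice. The day counts rest on the two assumed calendars, but the contrast between monthly steps and 12-weekly tests does not depend on the detail. The feasibility outcome and the analyses are untouched. This is a participant-safety procedure, which belongs in the protocol, and it should be settled before it is carried into the full-scale trial.

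**What to change.** (a) In section 7.1.2, have the physician issue a standing laboratory requisition with the three-step plan to any participant who meets section 9.1 (i) or (ii), with the instruction to have blood drawn 7 to 10 days after each RAAS inhibitor increase.

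(b) In section 7.1.2 and on the instruction sheet, if not already there, require the participant to notify the coordinator on the day of any home RAAS inhibitor increase. The coordinator then compares the latest potassium and eGFR with section 9.1, arranges the recheck if (i) or (ii) is met, and otherwise informs the physician, who decides under (iii).

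Part (a) covers those who meet a numerical criterion when the plan is written. Part (b) covers later changes and the discretionary recheck.

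The cost is a short addition to section 7.1.2, one line on the sheet and one brief message per home increase. If every step were a home increase, that is 17 × 3 = 51 messages for one full plan each, and at most 17 × 6 = 102 if a step followed all six measurement weeks. A few extra blood tests may result, all of them already provided for in section 9.1. The thresholds stay as they are and no clinic visit is added.

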### 9.2 Safety definitions

An adverse event (AE) is any untoward medical occurrence in a patient or clinical trial subject administered a medicinal product, which does not need to have a causal relationship with that treatment. Examples of study-specific AEs are laboratory abnormalities (see 9.1 above), symptoms of low BP or orthostatic hypotension.

A serious adverse event (SAE) is any adverse event that:

- Results in death
- Requires attendance at an emergency room or hospitalization (defined as admission to a medical facility for at least 24 hours)
- Any medically important events that, in the opinion of the local investigator, may
  jeopardise the participant or may require intervention to prevent one of the other
  outcomes listed in the definition above

# 9.3 Adverse event recording and reporting

The adverse event recording period will begin with entry into the study (day of randomization) and end on the last study visit approximately 26 weeks after randomization. All AEs will be recorded in the electronic CRF. Adverse events will be

captured by the site investigator or designee by inquiring about safety events since the last visit. Safety assessments may also be collected from participant report prior to the study visit by the patient contacting the research personnel, or by review of the clinical chart by the research personnel. Investigators have the primary responsibility for adverse event identification, documentation, grading, attribution of causality and reporting. AEs that are related to study treatment will be reported to the individual site's ethics board.

Local investigators will record the causality of the SAE in relation to the study treatment. Causality will be assessed as follows:

- Unrelated: There is not a reasonable possibility that the adverse event may have been caused by the study intervention.
- Possibly related: The adverse event may have been caused by the study intervention, however there is insufficient information to determine the likelihood of this possibility.
- Related: There is a reasonable possibility that the adverse event may have been caused by the study intervention.

When deciding about causal relationship, the investigator will consider whether the event may be the result of diseases or concomitant medications which typically can occur in this patient population such as: the natural progression of an existing disease, the development of a new and unrelated disease, or a known side effect of other concomitant therapies that the participant may be taking.

# 9.4 Data Safety and Monitoring Board (DSMB)

This study will be monitored by an independent DSMB consisting of 2 content experts (1 nephrologist and 1 hypertension expert) and a clinical epidemiologist. The DSMB will be blinded to the treatment allocation. The DSMB will be immediately informed of any SAEs which may potentially be related to the study intervention. Other SAEs will be reviewed during DSMB meetings. Interim reports, prepared by the data management team of the coordinating centre, for review by the DSMB will include data on recruitment, adherence and AEs. An interim report will be sent for review after 50% of

participants have been enrolled in the pilot trial. Should safety issues arise that the DSMB feel compromises the trial and/or participant safety, then a meeting of all coinvestigators will be convened to consider amending or stopping the trial.

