# 4.3 Randomization and allocation process

Randomization will be 2:1 intervention-to-control, and will be carried out with a web-based randomization system. A 2:1 allocation was chosen because there is already extensive experience of the usual care arm of the trial, and the intent is to determine the acceptability and safety profile of the intervention. The randomization website will be managed by the Data Management Services of the Ottawa Methods Centre Ottawa Hospital Research Institute. Randomization will be stratified by site (Ottawa versus Vancouver).

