# 4.4 Blinding and protection against bias

SMART-IgAN will be an open-label trial as there is no way to blind participants or investigators due to the nature of the intervention. The primary efficacy outcome is the achieved systolic BP which will be measured using an automated office BP measurement with the participant left unattended in the room. This is an objective measure that would not be influenced by knowledge of the intervention.

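### Section 9.4 blinds the DSMB to allocation and states no route to by-arm safety data; separately, the Visit 1 procedures omit the standing BP that Section 9.1 requires at every study visit

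*Protocol*

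**What the plan says.** **DSMB.** Section 9.4 sets up an independent board of three and states: "The DSMB will be blinded to the treatment allocation". Interim reports "for review by the DSMB will include data on recruitment, adherence and AEs", and one is due once half the participants are enrolled. SAEs that may be related to the intervention go to the board at once; other SAEs wait for its meetings. If the board sees a safety problem, the co-investigators meet to consider changing or ending the trial. Nothing is said about tables by arm, coded arms, or access to the codes.

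Three other sections bear on this. Section 9.1: "Participants in the intervention arm could be at a higher risk of adverse events from more rapid escalation of their anti-hypertensive therapy". Section 4.3, on the choice of 2:1: "the intent is to determine the acceptability and safety profile of the intervention". Section 4.4: "SMART-IgAN will be an open-label trial as there is no way to blind participants or investigators".

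**Orthostatic hypotension.** It is the first safety outcome listed under Section 3.2. Section 9.1 says: "Sitting and standing BP will be measured at each study visit to look for evidence of orthostatic hypotension". Section 8 defines those visits: "Participants will have three dedicated study visits embedded within their regularly scheduled clinic visits at baseline", then at 3 and 6 months; Section 4.2 agrees. The Visit 1 procedures describe the unattended automated reading and add: "This BP measurement approach is the current standard of care for all patients who attend the GN clinic and will serve as the baseline BP". They mention no standing measurement. Visits 2 and 3 both list the orthostatic test, and its method is first described under Visit 2.

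**The concern.** The first point is about what the board can judge while the trial runs. The protocol names a safety question with a direction: possibly more harm under self-management. It is a question about a difference between arms. The independent body asked to watch for it is denied the arm, while the investigators who treat the patients know it. With 2:1 allocation a raw count is hard to read, because most events would fall in the self-management arm even at equal risk. The board's opinion is also what triggers discussion of amending or stopping the trial.

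The second point does not depend on the first. Staff who work from the visit list would not take a standing BP at baseline; staff who work from Section 9.1 would. If it is not taken, a drop already present at entry and first found at week 12 looks the same as a new one. Adverse event recording starts at randomisation (Section 9.3), Section 9.2 gives orthostatic hypotension as an example of a study-specific event, and Section 7 allows antihypertensive treatment to change at study entry. A pre-change value could therefore not be recovered later.

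**Working it through.** The protocol gives no figure on either point and no expected event rates. The denominators below come from its design. Every event count and rate is an assumption.

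**Denominators.** Target 25 (Section 12.1), allocation 2:1 (Section 4.3).
- Final: 25 × 2/3 = 16.7, so about 17:8.
- Interim at 50% enrolled: 12.5, so 12 or 13 participants, about 8:4 or 9:4.

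**Share of events at equal risk.** 17/25 = 68% in the self-management arm.

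**What a total can and cannot show.** Suppose four participants have an event at the 8:4 interim. Given the total, the number in the self-management arm under equal risk is hypergeometric, with C(12,4) = 495 possible outcomes.
- 4/8 vs 0/4 (50% vs 0%): one-sided p = C(8,4)/495 = 70/495 = 0.14.
- 2/8 vs 2/4 (25% vs 50%): one-sided p = 1 − [C(4,4) + 8 × C(4,3)]/495 = 1 − 33/495 = 0.93.

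The total is four in both cases, but the direction is opposite.

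**What by-arm tables would add.** Power of Fisher's exact test, one-sided 0.05, by full enumeration:

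| Assumed rates (self-management vs control) | 8:4 | 9:4 | 17:8 |
|---|---|---|---|
| 20% vs 5% | 0.1% | 0.2% | 2.5% |
| 30% vs 10% | 0.7% | 1.7% | 10.2% |
| 40% vs 10% | 3.3% | 6.5% | 27.4% |
| 50% vs 10% | 9.6% | 16.7% | 49.0% |
| 60% vs 10% | 21.2% | 32.0% | 70.1% |

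At the interim the range is about 0.1% to 32%. The gain from by-arm data is therefore direction and context for each case, not a test.

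**Standing BP, sections side by side.**

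| Visit | Section 9.1 | Visit procedures in Section 8 |
|---|---|---|
| 1 (baseline) | required, since baseline is a study visit | not listed |
| 2 (week 12) | required | listed |
| 3 (week 24) | required | listed |

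The two sources disagree at Visit 1 only. For scale, one participant with a drop already present at entry that is found again at follow-up moves the control rate by 1/8 = 12.5 points, or the self-management rate by 1/17 = 5.9 points. Without a baseline value that case cannot be recognised as pre-existing.

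**The case against.** The strongest reply on the first point is that oversight does not rest on the board's arm comparison alone. Investigators know the arm, grade events and assign causality; related events go to the ethics boards; potentially related SAEs reach the DSMB at once. In a pilot of 25, by-arm tables would seldom settle anything statistically. All of this is correct, and it limits the point to the board's own view during the trial. It does not remove it: a board reviewing so few patients works from cases, direction and denominators, and the stated rule withholds the arm.

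A second reply is that Section 9.4 does not say reports are pooled, so coded A/B tables would be compatible with it. That is fair. The accurate criticism is that neither coded tables nor access to codes is stated.

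One might also argue that the blinding is only nominal, because adherence is measured only in the intervention group (Section 3.1) and notices of related SAEs hint at the arm. This is partly right. A summary of adherence does not label individual events, however, and case-by-case leakage supplies no denominators.

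On the second point, the reply is that Section 9.1 already requires the baseline measurement. It does, which is why the finding is a contradiction and not an absent measurement. Baseline values are also not needed for a valid comparison, since both randomised arms are tested at Visits 2 and 3. That stands.

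**Conclusion.** Both points hold, and they are independent of each other.

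1. As written, Section 9.4 leaves the DSMB unable to compare event rates between arms during the trial, in an open-label study that itself raises a possible excess in one arm. The size is shown by the 8:4 example, where the same four events fit 50% vs 0% or 25% vs 50%. The four events and the rates in the power table are assumptions, and the splits are rounded from 2:1.

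2. Section 9.1 and the Visit 1 procedures conflict on standing BP. The conflict decides whether a baseline value exists for the first-listed safety outcome.

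A reader might infer more, and the protocol does not support it:
- That the plan expects excess harm: Section 9.1 says only that the risk could be higher.
- That orthostatic hypotension has no baseline measurement: one section requires it and another leaves it out.
- That an excess could not be seen at all: unblinded investigators and immediate SAE notices give partial oversight, and the final randomised comparison stays valid.
- That the baseline gap contributes to what the DSMB cannot see: whether standing BP is taken at Visit 1 has no bearing on access to events by arm.

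**What to change.** **Section 9.4.** Replace the blinding sentence with a provision for closed DSMB reports that show AEs, SAEs, potassium, eGFR and orthostatic results by arm, with denominators. If the sponsor prefers coding, report by coded arm and state that the board may have the codes on request; 2:1 denominators would largely reveal the codes anyway. The cost is a change of wording and some extra tables from the data team that already prepares the reports.

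**Section 8, Visit 1, and Section 9.1.** Reconcile the two so that the Visit 1 list matches Section 9.1 on sitting and standing BP. With a baseline value in hand, report new-onset orthostatic hypotension as well as prevalence at weeks 12 and 24, so that pre-existing drops and chance imbalance at about 17:8 can be identified. The cost is a few minutes in a visit already planned to last one hour, plus one extra line in the safety table.
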